At the Centre Hospitalier Départemental (CHD) Vendée, an adapted physical activity is offered to fibromyalgia patients thanks to the "Siel Bleu" association group. This physical activity, carried out with patients suffering from different pathologies, is non-specific.

In parallel, a preliminary study has shown the benefit of lifestyle coaching with fibromyalgia patients, carried out by specifically trained physiotherapists, nurses and sports coaches, on quality of life (Hackshaw et al., 2016).

Another possibility seems to be to offer personalised coaching with a physical activity adapted to the patient's physical and organisational constraints, and specific to his or her pathology. This solution would make it possible to adapt to the patient's choice of physical activities, to ensure better adaptation to their physical and organisational constraints as well as better individualised follow-up.

1. RATIONALE FOR THE STUDY

1.1. POSITIONING OF THE RESEARCH

Fibromyalgia is a common, costly and controversial condition (Häuser et al., 2015; Häuser, Ablin, Perrot, & Fitzcharles, 2017). Häuser et al. report that most studies place the prevalence of this condition between 2 and 4% (Häuser et al., 2015). Two French studies estimate a prevalence of 1.4 and 1.8% (Bannwarth et al., 2017). (Bannwarth et al., 2009; Perrot, Vicaut, Servant, & Ravaud, 2011). The incidence would be 6.88% in men and 11.28% in women (Häuser et al., 2015).

Fibromyalgia is a complex syndrome, incorporating a wide range of symptoms and functional impairments (Fitzcharles et al., 2013; Häuser et al., 2015, 2017). While genetic, stress and environmental origins are mentioned, the inclusion of the central nervous system, with a "central sensitisation" to pain, seems a key element (Häuser et al., 2015). This formulation means that the central nervous system has a role in the modulation of pain (Williams & Gracely, 2006) and in the development of co-morbid symptoms (sleep disorder, fatigue, memory, depressed mood). In addition, there are two types of subjects, those with a trigger following a nociceptive input and those without a triggering history (Häuser et al., 2015). It is possible that the triggering mechanism of central sensitisation is different (i.e.: bottom-up¹ for the former and top-down for the latter).

The usual treatment consists of multimodal management: functional, psychological, pharmacological and socio-professional. The most common non-drug treatments are: pain education, cognitive-behavioural treatments, multi-component therapies (education or psychology combined with physical exercise) and aerobic exercise (Häuser et al., 2015). The dosage of this physical exercise should be adapted to the patient's health needs (Eijsvogels & Thompson, 2015). The currently recommended physical exercise is aerobic work combined with muscle strengthening (Bidonde et al., 2017; Häuser et al., 2017) with no evidence of superiority of effectiveness of one over the other (Macfarlane et al., 2017). In addition, dry and aquatic exercise appear to be equally effective (Bidonde et al., 2014; Macfarlane et al., 2017). The recommended dosage for aerobic exercise is 20 minutes (or twice 10 minutes), two to three times per week (70-80% of the Theoretical Maximum Heart Rate) and 8 repetitions per exercise 2 to 3 times per week (Bidonde et al., 2017; Macfarlane et al., 2017). At the CHD Vendée, fibromyalgia patients are offered adapted physical activity with the "Siel Bleu" association group. This group activity is non-specific since it is carried out with patients suffering from different pathologies. Moreover, this activity is limited by the material possibilities of the association group, which cannot move heavy equipment or instruments (elliptical, rowing machine, swimming pool, etc.). The choice was made to offer one endurance session per week with a ten-minute warm-up, forty minutes of *interval training* and ten minutes of rest. Participants can log on to the association's website to follow a complementary exercise programme if they wish.

¹ Bottom-up processes use information from the sensory organs and analyse the environment on the basis of this information, in contrast to top-down processes which use knowledge about the structure of the environment and influence perception.

According to Bennet et al. (2009), a 14% decrease in quality of life since baseline is considered clinically significant (Bennett, Bushmakin, Cappelleri, Zlateva, & Sadosky, 2009). Evaluated in a cohort study of 10 patients (Hackshaw et al., 2016) the interest of a 37% improvement in quality of life following lifestyle coaching by nurses, physiotherapists and adapted physical activity teachers, encourages us to propose personalised coaching with a physical activity adapted to the patient and specific to her pathology. We believe that this solution would allow for adaptation to the patient's choice of physical activities, but would also allow for better individualised follow-up and better adaptation to the patient's physical and organisational constraints, with a better medium and long-term impact on quality of life.

We hypothesize an improvement in the quality of life of fibromyalgia patients in the medium (6 months) and long term (12 months) thanks to personalized coaching (specific physical activity).

The objective of our study is to compare the impact of two physical activity management in fibromyalgia patients at 6 and 12 months:

- 1. Control group: Traditional non-specific management in a common "multipathology" group, with activity trackers**
- 2. Experimental group: Specific management in a "fibromyalgia patients" group, with activity trackers**

1.2. *BENEFITS AND RISKS FOR RESEARCH PARTICIPANTS*

Benefits

Individual benefit

Physical activity improves pain, quality of life and body mass quality of patients.

We expect this innovative health sport coaching to optimise these improvements (in quality of life, pain and body mass quality) compared to standard patient management.

Collective benefit

- This new treatment modality will improve the care available to the algologist for the treatment of his patients.

- We also wanted to evaluate a new, simple and rapid test of kinesiophobia using isochrony between an imagined movement and an executed movement to predict a patient's adherence to physical activity management. If this test is effective, it will allow better targeting of patients who can benefit from a rehabilitation programme using physical activity coaching.
- Finally, an evaluation of an innovative patient monitoring with impedancemetry should make it possible to propose new monitoring tools for evaluating patients with fibromyalgia.

Risks

No excess risk due to participation in the study is expected

In both arms of the study, the physical activity sessions are likely to cause more or less diffuse pain, aches, cramps, fatigue and discomfort. These symptoms are not specific to the study and are minimised by the supervision, which enables the absence of cardiac risk to be verified. Nevertheless, they may be felt as an increase in fibromyalgia pathology and experienced in a pejorative way by certain patients; this risk is minimised by the explanations provided within the framework of the research.

The constraints associated with attending the sessions and filling in the questionnaires were considered minimal, but could increase the anxiety of some participants.

Benefit/risk balance

The research manager qualifies the research in the first instance as **interventional research with minimal risks and constraints**, since :

- ✓ All procedures are performed in the usual way (*assessments, clinical examinations, interventions in physical activities*) and defined in the order of 12 April 2018 set by the Ministry.

The research does not focus on innovative or obsolete techniques or strategies.

Apart from the specialised physical activity offered to patients in the experimental group, the overall management of the patient will be identical to usual practice.

Consequently, the particular modalities of implementation in the research represent negligible constraints for the person who lends himself to the research. (Article R 1121-3 of the Public Health Code (CSP), decree n° 2006-477 of 26 April 2006).

The person in charge of the research will therefore, before any implementation of the research, submit the study protocol to the South-East III Committee for the Protection of Individuals (Comité de Protection des Personnes Sud-Est III) in accordance with Article L 1121-1 of the Version 3 of 02/10/2019

Page 9 on 33

Public Health Code (CSP) as they result from the laws n° 2004-806 of 9 August 2004 and n° 2006-450 of 18 April 2006 relating to public health policy, for a favourable opinion and confirmation of the research's qualification.

The bibliographical references are given in the annex to the document.

2. OBJECTIVES AND JUDGING CRITERIA

2.1. OBJECTIVE AND PRIMARY ENDPOINT

Main objective

To compare the benefit of a specific 6-month physical activity programme on **patients' quality of life**.

Primary endpoint

Evolution of the **Fibromyalgia Impact Questionnaire Revised** (FIQR) score (quality of life questionnaire specific to the management of fibromyalgia patients) between the beginning of the treatment (D0) and at 6 months (M6).

2.2. OBJECTIVES AND SECONDARY EVALUATION CRITERIA

Secondary objectives

Compare between the 2 randomisation arms:

1. The evolution of pain intensity between the beginning of the treatment (D0), at 6 months (M6) and at 12 months (M12),
2. The presence of neuropathic pain and its evolution,
3. The evolution of isochrony between a physically executed and mentally simulated movement (Moseley, 2004; Moseley et al., 2008)
4. The evolution of anxiety and the presence of signs of the depressive series
5. The evolution of pain on muscle compression

6. The severity of the symptoms
7. Monitoring physical activity with activity trackers
8. The evolution of lean body mass measured on an impedance scale
9. The evolution of kinesiophobia
10. Changes in quality of life between the start of treatment (D0) and 12 months (M12)
11. Continuity of physical activity after the end of coaching

Secondary evaluation criteria

1. EVA at D0, M6 and M12
2. DN4 questionnaire score ≥ 4 at D0, M6 and M12
3. Difference between the duration of the performed movement and the imagined movement of picking up a magazine from a table at D0, M6 and M12
4. Hospital Anxiety and Depression scale (HAD) at D0, M6 and M12
5. Widespread Pain Index (WPI) (Häuser et al., 2017; Wolfe et al., 1990) at D0, M6 and M12
6. Symptom Severity Scale (SSS) (Häuser et al., 2017; Wolfe et al., 1990) at D0, M6 and M12
7. Percentage of success in achieving goals each month (M1-M12) as measured by activity tracker
 - (Duration in minutes per month at least 70% of the theoretical maximum heart rate $\times 100 / 240$ minutes
 - (4 weeks \times 60 minutes recommended = 240 minutes)
8. Percentage and weight of lean mass measured on an impedance scale at D0, M6 and M12
9. Tampa self-questionnaire (Knapik, Saulicz, & Gnat, 2011) at D0, M6 and M12
10. FIQR at D0 and M12 and EQ5D-5L at D0, M6 and M12
11. Level of physical activity between the groups between M6 and M12
 - (the duration in minutes per month between 50 and 60, between 60 and 70, between 70 and 80, between 80 and 90, and between 90 and 100% of the theoretical maximum heart rate measured with the activity tracker)

Exploratory secondary objective

Evaluating the isochrony between a physically performed and mentally simulated movement as a predictive test of improved quality of life following a physical activity programme Isochrony will be assessed by the difference between the duration of the performed movement and the imagined movement of taking a review on a table at D0. The quality of life of the patients will be assessed from the FIQR score at M6 and M12.

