4.3. RESEARCH AND ANALYSIS TECHNIQUES

Detailed description of the evaluation parameters

The revised Fibromyalgia Impact Questionnaire (FIQR, Appendix 5) is a self-administered questionnaire to assess the quality of life of the fibromyalgia patient (Burckhardt, Clark, & Bennett, 1991). Composed of 10 items, the first item includes eleven questions rated from 0 to 3 on a Likert scale. Items 2 and 3 ask the patient to indicate the number of days they felt well and the number of days they were unable to work (including housework) due to fibromyalgia symptoms. Items 4 to 10 are horizontal linear scales marked in 10 steps on which the patient rates work difficulties, pain, fatigue, morning fatigue, stiffness, anxiety and depression. The Minimum Clinically Important Difference is 14%. (Bennett et al., 2009). This means that a 14% difference in the FIQR score is clinically important.

The Visual Analogue Scale (VAS) of pain is used to assess the progression of pain (Scott & Huskisson, 1976). . The therapist should explain the use of the scale by presenting the ruler with the extremes: "You have to move the cursor, with no pain on the left and the maximum pain you can imagine on the right". It is marked from 0 to 100 on a ruler, the patient must move a cursor on the side without graduation. The therapist reports the intensity of the pain felt on the graduated side. The Minimum Detectable Change is 11, while the Minimum Clinically Important Difference is 13.7 points out of 100. The evaluation of the pain will be done on the different areas of pain felt by the patient (cervical, limb).

The DN4 questionnaire (Appendix 6) is used for the detection of neuropathic pain. The first part is based on the history, the second on a clinical examination. This questionnaire is administered by the therapist. If the score is greater than or equal to 4/10, the test will be considered positive (Bouhassira et al., 2005).

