All variables will be described globally and by group. The description will include the numbers and percentages of modalities for qualitative variables and the minimum, maximum, mean, standard deviation and median for quantitative variables.

Main criterion

The patients' quality of life will be measured using the FIQR questionnaire at D0, M6 and M12. The evolution of the score at 6 and 12 months will be characterised by a graph and compared between the 2 groups using a linear regression model taking into account the baseline score at D0, the time effect, the "time*group" interaction and the repeated nature of the data.

The comparison of the evolution of the score at M6 will be tested from the M6 contrast.

Secondary criteria

The evolution of pain will be graphically characterised and compared using a mixed linear regression model taking into account the baseline data of the D0 score and the repeated nature of the data.

Neuropathic pain will be assessed using the DN4 questionnaire score. It will be compared between the two groups using a mixed generalized linear regression model taking into account the repeated nature of the data.

The evolution of the isochrony will be characterised graphically and compared using a mixed linear regression model taking into account the baseline data J0 and the repeated nature of the data.

The evolution of anxiety will be assessed from the total HAD score and compared between the two groups using a mixed linear regression model taking into account the baseline D0 score and the repeated nature of the data.

The evolution of pain on muscle compression will be assessed from the total WPI score and compared between the two groups using a mixed linear regression model taking into account the baseline score on D0 and the repeated nature of the data.

The severity of symptoms will be measured from the SSS score and compared using a mixed linear regression model taking into account the baseline data of the D0 score and the repeated nature of the data.

Physical activity monitoring will be collected every month until M12. Each month, the percentage of goal achievement will be calculated. The average percentage of success will be plotted and compared between the 2 groups using a mixed linear regression model taking into account the repeated nature of the data.

The evolution of lean body mass will be collected at D0 M6 and M12 and compared using a mixed linear regression model taking into account the repeated nature of the data.

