
The evolution of kinesiophobia will be assessed using the TAMPA self questionnaire at D0, M6 and M12. The total score will be compared between the groups using a mixed linear regression model taking into account the baseline score on D0 and the repeated nature of the data.

The evolution of the quality of life will be measured using the EQ5D-5L questionnaire at D0, M6 and M12. The evolution of the score will be characterised by a graph and compared between the 2 groups using a mixed linear regression model taking into account the baseline score on D0 and the repeated nature of the data.

Exploratory criterion

The evolution of the FIQR score will be evaluated using a linear mixed model taking into account the group and repeated nature of the data as well as the isochrony data at D0 in order to evaluate its predictive character.

Statistical justification of the number of inclusions

The study is a superiority trial on the decrease of the FIQR score (improvement of the quality of life) at 6 months between a control group (classic non-specific management in a common "multipathology" group) and an experimental group (specific management in a "fibromyalgia patients" group).

According to Hackshaw et al. (2016), the mean baseline QoL of the ten patients included was 49.4 (13.8) on the FIQR scale. After 6 months of intervention (life coaching including physical activity), the mean level of quality of life was 31.0 (13.2), i.e. a decrease in score of 18.4 points (37% decrease).

Evidence of a 7-point difference between the two intervention groups at M6 will be considered clinically significant.

With a power of 80%, and an alpha risk of 5%, 114 patients will be needed to show this difference. To ensure the necessary power, an additional 10% of patients will be included, for a total of 126 patients.

Expected level of statistical significance

The alpha risk is set at 5%.

Statistical criteria for stopping the research

NA

Method of accounting for missing, unused or invalid data

All missing data and the reason for it will be described in each group.

The FIQR score will be estimated and compared between the 2 groups using a linear model taking into account the repeated nature of the data, so no imputation method will be applied.

Managing changes to the original strategy analysis plan

NA

Selection of persons to be included in the analyses

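### DN4 ≥ 4 is the only criterion named for the evolution of neuropathic pain; the 0–10 score already collected should be compared as well

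*Combined protocol and SAP*

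**What the plan says.** Section 2.2, secondary objective 2, is to compare between arms "The presence of neuropathic pain and its evolution". The matching criterion 2 is "DN4 questionnaire score ≥ 4 at D0, M6 and M12". No other criterion is listed for that objective.

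Section 4.3 presents the DN4 as an instrument for detecting neuropathic pain, scored out of 10: "If the score is greater than or equal to 4/10, the test will be considered positive".

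Section 5.2 (secondary criteria) says "Neuropathic pain will be assessed using the DN4 questionnaire score" and that the arms will be compared with a "mixed generalized linear regression model taking into account the repeated nature of the data". It does not repeat the cut-off, and it names no distribution or link.

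The other scales are handled differently in 5.2. Pain, HAD, WPI, SSS and Tampa each get a mixed linear model on the score, adjusted for the D0 value. Tampa is the closest parallel: section 4.3 gives it a threshold too (40/68), but 5.2 compares its total score.

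**The concern.** Objective 2 asks two questions. Presence is a yes/no matter, and a detection threshold answers it. Evolution is a matter of change, and a positive/negative status records change only when a patient crosses 4. A fall from 9 to 4 is scored as no change, while a fall from 4 to 3 is scored as full resolution. A patient below 4 at D0 can become positive but cannot register an improvement, and section 3.2 sets no DN4 threshold for entry, so such patients can be enrolled.

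The finer information costs nothing to obtain, because the score out of 10 exists at all three visits. If treatment produces graded change, a comparison limited to the cut is less likely to show it. A null result could then be read as no effect on neuropathic pain.

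There is also a drafting gap. Section 2.2 names a status and section 5.2 names a score, so the analysed variable is not fully settled.

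**Working it through.** **Step 1. Which variable is analysed?** Criterion 2 is a threshold. Section 5.2 gives the DN4 a generalized linear mixed model and gives the scores listed above a mixed linear model. Together these point to a binary outcome. Against that, 5.2 uses the word score and states no link. Binary is therefore an inference, although the likelier one.

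**Step 2. Sample size.** The only sample size in the plan is for the FIQR: "With a power of 80%, and an alpha risk of 5%, 114 patients will be needed to show this difference". The target is 7 points: "Evidence of a 7-point difference between the two intervention groups at M6 will be considered clinically significant". The SD used is not named; 13.2 is the 6-month SD of the pilot study cited in 5.2. With two-sided 5% (sidedness is not stated) and 80% power:

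n per arm = 2 × (1.96 + 0.8416)² × (13.2/7)² = 55.8, so 56. The t-test version gives 56.8, so 57 per arm, which is 114. The plan's figure reproduces. The baseline SD of 13.8 gives 62 per arm (124) and does not. Adding 10%: 114 × 1.10 = 125.4, so 126.

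This supplies n = 57 per arm. It says nothing about power for the DN4.

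**Step 3. Assumptions for the DN4.** The documents give no DN4 mean, SD, share positive or expected effect. Assumed: SD 2, control mean 3 to 6 at M6, and a standardised effect d of 0.2, 0.3 or 0.53. The last is the FIQR target, 7/13.2, borrowed for illustration only.

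**Step 4. Uniform shift, closed form.**

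- Score: power = Φ(d√(n/2) − 1.96). For d = 0.53: 0.5303 × √28.5 = 2.83, and Φ(0.87) = 0.81.
- Cut: a rounded score of 4 or more means an underlying value of 3.5 or more, so p = 1 − Φ((3.5 − mean)/2). With p̄ the average of the two arms' proportions, power = Φ{[|p₁ − p₂|√n − 1.96√(2p̄(1 − p̄))] / √[p₁(1 − p₁) + p₂(1 − p₂)]}.
- Example, control mean 4 and d = 0.53: p₁ = 0.60 and p₂ = 0.39, giving power 0.61.

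| Control mean (share ≥ 4) | d = 0.2: score / cut | d = 0.3: score / cut | d = 0.53: score / cut |
|---|---|---|---|
| 3 (40%) | 19% / 13% | 36% / 23% | 81% / 57% |
| 4 (60%) | 19% / 13% | 36% / 24% | 81% / 61% |
| 5 (77%) | 19% / 12% | 36% / 22% | 81% / 57% |
| 6 (89%) | 19% / 10% | 36% / 17% | 81% / 45% |

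**Step 5. Uniform shift, simulated integer scores.** Scores were rounded and limited to 0–10, with a t-test on the score and a two-proportion test on ≥ 4. Rounding and limiting the range lower the power of the score slightly.

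- 0.2 SD: about 18% against 10–13%, a loss of about 5–8 points.
- 0.3 SD: about 35% against 17–25%, a loss of about 10–18 points.
- 0.53 SD: 77–80% against 46–62%, a loss of about 18–34 points.

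**Step 6. A different pattern of effect.** Suppose instead two groups with DN4 means 2 and 6 and within-group SD 1 to 1.3, where treatment lowers the share in the high group from 60% to 35%. Power is then about 62–67% on the score and 63–71% on the cut. With 50% to 25%, or 70% to 45%, the score is at most about 1 point better and the cut up to about 4 points better. There is no meaningful loss.

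Steps 4 to 6 are unadjusted single-visit tests at M6, not the planned repeated-measures model.

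**The case against.** The best defence is that the cut fits the objective. Evolution of presence can be read as status over time. For a detection test, 9 to 4 is still positive and 4 to 3 is no longer positive, which is what such a test should report. Section 4.3 describes the DN4 as a detection tool. It gives important-difference values for the FIQR and the pain VAS but none for the DN4, so a mean DN4 difference would have no stated interpretation. Pain intensity is already compared quantitatively under objective 1. All of this stands as a reason to keep the cut. It does not show that a threshold crossing should be the only measure of evolution.

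Three stronger readings are tempting, and the documents do not support them.

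- **That the comparison loses about 20 points of power.** That figure needs about 80% power on the score, a cut near the middle of the distribution and a uniform shift. No DN4 input in the documents establishes any of these, and step 6 shows a plausible pattern with no loss.
- **That a real difference will probably be missed because of the cut.** At 0.3 SD both forms are weak (about 35% against 17–25%), and patients who start below 4 still contribute because they can become positive.
- **That the plan certainly analyses only the binary form.** Section 5.2 says score and leaves the link open. An ordinal model on the score could be fitted in the same framework.

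**Conclusion.** The point holds as a cheap improvement. As written, DN4 ≥ 4 is the only criterion named for the evolution of neuropathic pain, and the model in 5.2 most naturally analyses that status. The cut is appropriate for presence. For evolution it discards changes that do not cross 4, and the plan gives no reason for treating the DN4 differently from HAD, WPI, SSS and Tampa.

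The cost in power cannot be fixed from the documents. It runs from nothing, if patients move between well-separated groups, to about 18–34 points, if a uniform shift of 0.53 SD applies, under the assumptions in the working (57 per arm, SD 2, control mean 3–6). Which pattern holds is unknown, and that is a reason to report both forms. The DN4 is a secondary outcome with no stated power target, so the primary FIQR analysis and the sample size are untouched.

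**What to change.** Align sections 2.2 and 5.2 so that each half of objective 2 has its own named variable and model:

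- **Presence:** keep the proportion with DN4 ≥ 4 by arm and visit, compared with a mixed model for a binary outcome, with the link stated.
- **Evolution:** add a between-arm comparison of the 0–10 DN4 score at M6 and M12, using the mixed linear model with D0 adjustment already planned for the other scale scores, or an ordinal mixed model if the distribution is skewed.

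This takes about one sentence in each section. It needs no new data and no extra patient burden, because a score out of 10 is already obtained at each visit. The downsides are one more secondary analysis and a mean difference for which the protocol gives no important-difference value. Keeping the proportion positive alongside it helps with the second.
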